B] Allocation concealment mechanism:

The supervisor of the study will write the randomization numbers of the patients in opaque white papers folded three times to form sealed envelopes and store it inside a box. Then will keep the Codes for randomization at the secretary office.

C] Implementation:

At time of intervention, the main operator will send the patient to the secretary office. Then, the assigned employee will open the box and ask the patient to select one envelope. the main operator will assign each participant for the

corresponding intervention either (friction or frictionless group) according to the list of codes of randomization.

Assignment to either intervention will occur before leveling and alignment stage.

D] Blinding:

Blinding of the operators: Blinding will not be possible for the operators during the application interventions and during the follow up visits. The principal operator is responsible for assigning subjects to interventions according to the concealed allocation, appliance activation at follow up visits, dental impressions and acquisition of dental casts.

Blinding of the outcome assessors: It is a single blinded study, the outcome assessors only will be blind. The patients name will be sealed from pre and post study models. Then two assessors will carry on, blindly and independently, the measurements and analysis of the study.

III) Data collection, management and analysis:

A] Data collection methods:

Primary outcome:

1. Retraction rate: to assess the antero-posterior movement of anterior teeth and first molars, the principle investigator will take study models for every participant monthly during the follow up visits. Then will digitize the models and identify the landmarks, reference lines and planes on the pre, interim and post-retraction digital dental models for measurements reading.

Secondary outcomes:

- 1. Anchorage loss:*** will be accessed by the principal investigator via scanned study models before and after the completion of retraction by identifying the landmarks, reference lines and planes, then will interpret the measurements in degrees and millimeters.
- 2. Pain:*** Each patient will fill a questionnaire regarding his treatment experience in a VAS scoring from 1-10. The questionnaire will include several questions related to oral hygiene, pain and discomfort experienced throughout the trial.

B] Data management:

A colleague outside the research team will enter the data and organize it in excel sheets in the computer of the orthodontic department.

Data will include all photographs, models, radiographs and filled questionnaire.

C] Statistical Analysis:

- The principle investigator will be responsible for the extraction of the required data from the study models taken at every follow up visit. The data will be sent to a specialized statistician.
- The specialized statistician will be responsible for the statistical analysis of the study by:
 1. Presenting the data as mean, standard deviation (SD) and Standard error (SE) values.
 2. Using Paired t-test to compare between the friction and the frictionless group of retraction as well as to compare between the pre-and post -treatment data for each group.
 3. Using Kolmogorov Smirnov and Shapiro Wilk tests to determine the rate of anterior segment retraction.

4. Statistically evaluate the patient acceptance for both techniques.

- For this study, the specialized statistician will use IBM11 SPSS12 Statistics Version 20 for Windows to perform the required statistics.
- The significance level will be $P \leq 0.05$. Highly significant variables are detected when P value is less than 0.01.

Assessors Reliability:

- To achieve high reliability for measurements, the supervisor will choose a well-experienced inter-examiner during the study.
- A training session will be provided for the examiners to ensure standard measurements techniques.
- Each examiner will complete the measurements on a model and will repeat the procedure after one week to assess the intra- and inter-examiner reliability.
- The supervisor will compare the measurements of the two assessors for disagreement with a difference of more than one millimeter.
- The supervisor will evaluate the amount of variation in measurements among and between examiners to test the performance of each assessor.
- The examiner with less reliability will receive additional training but will be replaced during the study.
- The specialized statistician will calibrate the intra and inter-examiner reliability for the measurements of the study by Inter-observer and intra-observer reliability was assessed using $P \leq 0.05$.

IV) Method Monitoring:

A] Data Monitoring: An independent Data Monitoring Committee (DMC) will monitor the results of the study. The Committee will include the trial's supervisors, who will periodically review the trial data and identify the need for any adjustments or modifications during the study.

B] Interim Analysis: no interim analysis will be performed during the study.

C] Harm: The main operator will document and report any harms or unwanted effects during the study intervention to the trial supervisors. Also any unpleasant

experience will be reported by the patient in the final questionnaire at the end of the retraction. The main operator will be responsible for the management of any adverse effects or unfavorable side effects resulting from the appliance.

D] Auditing: The supervisor will follow up and review the different interventions and resulting data. And he will periodically follow up the trial progress including recruitment of patients, allocation of participants to study groups; adherence to interventions and reporting of harms. A meeting with the senior supervisor will be set every 3 months to monitor the progress of the study and the need for any adjustments.

V) Ethics and dissemination:

A] Research Ethics Approval:

The Ethical committee in Future University, Egypt will review the protocol before they approve it. The research Ethics committee will evaluate the different interventions of the study to ensure its ethical validity and the potential benefits to the participants.

B] Protocol amendments:

The main investigator will be responsible to complete a formal amendment in case of any modifications or adjustments to protocol that may affect the conduct of the study, as changes in the study design or intervention procedures. The Orthodontics department, Faculty of Oral and Dental Medicine, Future University and the Ethics Committee will approve such amendment before proceeding in the study .

C] Consent:

The main investigator will be in charge for detailed explanation and elaboration of the different steps of the study interventions for each patient. Then will ask every participant to sign a written consent before they begin treatment. The consent will be written in Arabic.

D] Confidentiality:

The main investigator will store any personal information about the participants collected during the study separately from study records in locked files in areas with only access to the supervisors responsible for auditing and analysis. Also, will keep the files in the Department Of Orthodontics, Faculty of Oral and Dental Medicine, Future University and will identify all the reports, data and administrative forms by a coded ID number to maintain participant confidentiality. Participant information won't be used outside the study except with written permission of the participant.

E] Declaration of interests:

No financial interests are to be declared by the supervisors and the principle operator. This study is a part of a Masters' degree in Orthodontics, Faculty of Oral and Dental Medicine, Future University and it is self-funded by the principal investigator.

F] Access to data:

The supervisors and the principal investigator will only have access to the data of the study. All the data will be secured by a password to maintain confidentiality. No other parties are allowed to assess the results until the study is terminated and the conclusions are revealed.

G] Ancillary and post-trial care:

Any complication associated with the intervention will be managed by the principal operator. Then the two group of patients will continue their regular orthodontic treatment according to the treatment plan described for each case.

H] Dissemination Policy:

The trial results will be available to the participants, health care professionals and the public by publication of the study in high quality national and international journals. The principal investigator will present a copy of the thesis at the Faculty of Oral and Dental Medicine, Future University library and will distribute additional copies among the main universities in Egypt.

References

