- **Primary Outcome:** measuring the rate of anterior segment retraction for space closure when frictionless and friction mechanics were used.

Secondary Outcomes: measuring the changes in incisal position with regards to tip, torque and vertical position following

Outcome measure:

Outcome measure	Measure tool	Measure unit
1 ^{ry} Outcome	Assess the rate of anterior segment retraction	Digital scanned dental models. mm
2 ^{ry} Outcomes	1) Assess amount of anchorage loss.	Digital scanned dental models. mm
	2) Pain	Pain scoring sheets given to patients. VAS scoring from 1-10

B-Research question:

In orthodontic adolescent patients in need of 1st premolar extractions followed by anterior segment retraction, is there a difference, in terms of rate of anterior segment retraction, between friction and frictionless mechanics?

Objectives of the study

Research hypothesis:

The null hypothesis of this research is that there is no difference in rate of anterior segment retraction between friction and frictionless mechanics.

Primary objective:

Measuring the rate of anterior segment retraction using frictionless versus friction mechanics.

Secondary objectives:

Assess amount of anchorage loss and pain experienced.

Study design:

This is a randomized clinical trial with two arms parallel group and 1:1 allocation ratio. In one group, frictionless mechanics will be applied during anterior segment retraction while the other will receive friction mechanics during retraction to compare the results for differences in rate.

Materials and Methods

I)participants, interventions, and outcomes

A] Study Setting:

The study will be performed in the clinic of the Orthodontic Department at the Faculty of Oral and Dental Medicine, Future University. The recruited sample would be from the Egyptian urban and rural population.

B] Eligibility criteria:

- **Inclusion criteria:** for the participants include the following:
 1. Adolescent patients (females only).
 2. Patients requiring 1st premolars extraction followed by anterior segment retraction.
 3. Patients with fully erupted permanent teeth (not necessarily including the 3rd molar).
 4. Cases requiring maximum anchorage during anterior segment retraction.

- **Exclusion Criteria:** for the involved subjects included:
 1. Patients suffering from any systemic diseases interfering with tooth movement.
 2. Patients with extracted or missing permanent teeth. (except for third molars).
 3. Patients with badly decayed teeth.

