- Crimbable hooks added to the arch wire (0.017"x0.025" Stainless steel) distal to the lateral incisor passing through the center of resistance of the anterior segment.
- A ligature wire extending between the canines and mini-screws will be used for proper anchorage control.

- Retraction will start on a 0.017"x0.025" Stainless steel wire with an elastomeric power chain (force applied will be 160 g) extending between the crimpable hooks and the mini-screws.
- The force will be measured by a force gauge and reactivated each visit to maintain force of retraction constant all over the retraction phase.

➤ **Follow up visits**

Patients will be asked to attend for follow up sessions every 4 weeks for:

- Evaluation of the mini implants stability.
- Replacement of the power chain to maintain a force of 160g.
- Reactivation of the T-loop by further distal activation and cinch back.

➤ **Criteria for discontinuing or modifying the allocated intervention:**

In cases of prolonged swelling or pain related to the miniscrew the patient will be given strict oral hygiene measures and may wait for three weeks before the beginning of retraction.

In cases of loose or broken miniscrews, the screw will be removed and replace the miniscrew after total resolution of the inflammation.

➤ **Post-retraction Questionnaire:**

The patients of both groups will be asked to fill in questionnaires regarding their experience with both techniques.

➤ **Retraction records**

The scanned dental models will assess the rate of retraction and molar anchorage loss achieved throughout the study.

➤ **Material Used**

- American Orthodontics Brackets, Roth prescription, Bidimensional slot size.
- American Orthodontics Elastomeric power chains
- American Orthodontics Elastomeric O-ties
- American Orthodontics Ligature wire.
- Jeil, Mini Screws, 8 mm length.
- American Orthodontics Arch wires.
- American Orthodontics Molar bands/tubes.

D] Outcomes

[figure not shown]
Primary outcome: is to monitor the rate of anterior segment retraction using both frictionless and friction methods.

Secondary outcomes is to monitor anchorage loss and pain, in association with each technique after retraction during anterior segment retraction,. All outcomes will be assessed as the difference between T_0 at the start of anterior segment retraction after full canine retraction and T_{final} after complete space closure.

E] Participant timeline:

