1. The principle investigator will screen the potential patients through careful clinical examination of patients at the orthodontic department, Faculty of Oral and Dental Medicine, Future University.

2. All recruited patients should fulfil the previously mentioned inclusion and exclusion criteria.
3. Every participant will be asked to sign an informed consent before the beginning of the study.
4. After patient's enrolment, each participant will be asked for pre-intervention records to ensure proper diagnosis.
5. The supervisor will randomly allocate the patients to one of the intervention groups.
6. Active intervention will begin after proper leveling and alignment of the upper and lower arches and canine retraction.
7. The principle investigator will take pre-retraction records for every participant. (T_0)
8. In Friction mechanics group, Power chain is used for anterior segment retraction while in Frictionless group, T-loop is used for retraction.
9. Each patient will come every 4 weeks for follow up visit, for appliance activation and uptake of impression for interim records.
10. After complete space closure, the principle investigator will take post-retraction records for each participant. (T_{final})
11. Every patient will fill up a questionnaire regarding his experience during treatment.
12. The principle investigator will continue the normal treatment and achieve proper finishing for every patient after the end of the study.

CONSORT flow chart of the flow of participants in the study.

E] Sample size calculation:

Our sample size calculation is based on a previous study comparing the effect of friction and frictionless mechanics. [14]

F] Recruitment strategy:

The principal investigator will recruit the patients from the clinic of Orthodontic department, Faculty of Oral and Dental Medicine- Future University.

Screening of patients will continue until the total number of participants for the study is collected.

II) Assignment of interventions:

A] Sequence generation:

The supervisor of the study will apply Computer generated random numbers to randomly assign patients to Group A (Friction) or B (Frictionless) using Microsoft Office Excel 2007 sheet. and will write the patient numbers in the first column, and will select function RAND() to generate the randomization number in the second column. These numbers will be sorted according to the randomization number so the first column numbers will be randomly distributed.

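### The primary outcome is a rate, but the stated assessment rule and unit carry no time, no readable text gives a rate formula, and the named tests do not fit

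*Combined protocol and SAP*

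**What the plan says.** The Research hypothesis section reads: "The null hypothesis of this research is that there is no difference in rate of anterior segment retraction between friction and frictionless mechanics". The primary outcome row of the Outcome measure table reads "Assess the rate of anterior segment retraction", with tool and unit given as "Digital scanned dental models. mm". Section D] Outcomes repeats that the primary outcome "is to monitor the rate of anterior segment retraction using both frictionless and friction methods", then adds "All outcomes will be assessed as the difference between T_0 at the start of anterior segment retraction after full canine retraction" and a final record taken once the space is fully closed.

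Other passages describe serial data:

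- The Retraction records paragraph says the scanned models serve to assess both the retraction rate and molar anchorage loss over the course of the study.
- Participant timeline, item 9: "Each patient will come every 4 weeks for follow up visit, for appliance activation and uptake of impression for interim records". Item 10: "After complete space closure, the principle investigator will take post-retraction records for each participant".
- Data collection methods, primary outcome: monthly models are digitised and landmarks identified on the pre, interim and post models, to assess antero-posterior movement of the anterior teeth and first molars. The paragraph stops there.
- Statistical Analysis: the data for the statistician come from the models of each follow-up visit.

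The Study design section states: "This is a randomized clinical trial with two arms parallel group and 1:1 allocation ratio". Statistical Analysis item 2 names a paired t-test both for friction against frictionless and for pre against post within each group. Item 3 assigns the Kolmogorov-Smirnov and Shapiro-Wilk tests to determining the rate.

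**The concern.** A rate needs a distance and a time. The rule in D] Outcomes supplies only a distance, and its end point is an event, so the time taken drops out. Taken literally, that rule does not test the stated null hypothesis. If it is set aside in favour of the serial models, the analyst must still decide which scans count, how to turn them into one number and what to do about closure between visits. None of this is fixed in the readable text, so it could be settled after the data are seen.

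The tests do not close the gap. A paired t-test between arms needs a partner for each patient, and a parallel-group design without matching provides none. The normality tests describe the shape of a distribution; they neither estimate nor compare a rate. Item 3 is the only analysis item that names the rate, so the primary hypothesis has no suitable between-arm test.

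**Working it through.** The readable text gives no sample size, effect, SD or starting space for the primary outcome, so there is no figure of the plan's own to reproduce. All numbers below are illustrations on stated assumptions.

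**1. The start-to-closure difference.** Assume 4 mm of anterior retraction in each of two patients.

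- Closed in 4 months: difference 4 mm; rate 4/4 = 1.0 mm/month.
- Closed in 8 months: difference 4 mm; rate 4/8 = 0.5 mm/month.

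The rule scores them alike. Equal spaces imply equal retraction only if the molars do not move forward. With anchorage loss the difference in mm could vary between arms, but it would then reflect distance and still not speed.

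**2. What a test on that difference detects.** Assumptions: retraction distance mean 4 mm, SD 0.7, equal in both arms; rates 0.87 and 1.27 mm/month, SD 0.34; 20,000 simulated trials per setting. The 0.87 and 0.34 are taken from a canine-retraction trial in the literature review and are not planning values; the 0.40 difference is assumed.

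| Per arm | Unpaired test on mm: rejects | Unpaired test on mm/month: power | Paired test on mm/month: power |
|---|---|---|---|
| 10 | 5.0% | 71% | 65% |
| 15 | 5.1% | 87% | 84% |
| 20 | 4.8% | 95% | 94% |
| 30 | 4.5% | 99% | 99% |

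Under these assumptions the test on distance has no power beyond its 5% error rate. With no true difference in rate, the paired test rejected in 5.0% to 5.4% of trials.

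**3. The rate formula matters.** For assumed monthly movements of 1.2, 1.0, 0.8, 0.5, 0.3 and 0.2 mm (total 4.0 mm over 6 months):

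- total over time: 4.0/6 = 0.67 mm/month;
- least-squares slope: 0.66;
- median interval: 0.65;
- first interval: 1.20.

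The first three nearly agree here; the fourth does not.

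**4. Arbitrary pairing.** With equal SDs in the arms, paired t = unpaired t / √(1 − r), where r is the chance correlation that the pairing creates. With 10 per arm, an unpaired p of 0.05 means t = 2.101 (18 df), and the paired test has 9 df. Chance correlations for 10 unrelated pairs lie between −0.632 and +0.632 in 95% of pairings.

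- r = −0.632: t = 2.101/√1.632 = 1.645, p = 0.13.
- r = 0: t = 2.101, p = 0.065.
- r = +0.632: t = 2.101/√0.368 = 3.463, p = 0.007.

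Random re-pairing of simulated data agrees: the central 95% of paired p-values is about 0.01 to 0.13 with 10 per arm and 0.01 to 0.11 with 20. The middle half is about 0.04 to 0.09 and 0.04 to 0.08.

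**5. Precision of a per-patient slope.** Standard error = scan error SD / √Sxx, for T0 plus k scans spaced 28/30.44 = 0.920 month apart. Assumed scan error SD: 0.1 to 0.3 mm.

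| k | Sxx | Standard error, mm/month |
|---|---|---|
| 1 | 0.423 | 0.15 to 0.46 |
| 2 | 1.69 | 0.08 to 0.23 |
| 4 | 8.46 | 0.03 to 0.10 |
| 8 | 50.8 | 0.01 to 0.04 |

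A 4 mm space gives 4 scans before closure at 1.0 mm/month and 8 at 0.5. Precision therefore depends on the rate itself and may differ between arms.

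**The case against.** The best defence is that one general sentence is being set against everything the plan says about data collection. The Retraction records paragraph, timeline item 9, the Data collection section and the Statistical Analysis section all point to a rate read from serial models, and visits are dated, so elapsed time can be recovered. That stands, and it rules out the inference that the trial cannot measure a rate. What is missing is a definition. The defence also shows that the rule in D] Outcomes is not cleanly the rule for anchorage loss: Retraction records ties anchorage loss to models throughout the study, and the primary-outcome paragraph includes the first molars.

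A definition might also sit in text that cannot be read. The figure under D] Outcomes is not shown and the outcome table is broken. The finding is therefore limited to readable passages. A figure would still not change the all-outcomes sentence or the tests in items 2 and 3.

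Three further inferences go too far. A reader might suppose that the paired test inflates false positives; with pairing fixed in advance it does not, and the power loss in the table is about 5 points at 10 per arm, 3 at 15 and 1 or less from 20. A reader might suppose that the formula will be picked after the data are seen; the documents show only that it could be. And a reader might compute a bias from dividing distance by the time to the visit at which closure is first seen, but the plan never adopts that formula.

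**Conclusion.** The concern holds, and it must be fixed because it affects the primary outcome and its only between-arm test. Read literally, the start-to-closure rule and the mm unit do not test the stated null hypothesis. Read charitably, a rate is intended and obtainable but undefined in the readable text.

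The parts carry unequal weight. The missing rate definition matters most. The paired test is an error for unmatched parallel arms: its practical cost is a p-value that depends on who is paired with whom, plus a modest loss of power. The normality-test item is mainly a wording correction.

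The contradiction itself rests on the text alone. The sizes rest on assumed distances, rates, SDs and arm sizes, and should not be read as predictions for this trial.

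**What to change.** 1. In D] Outcomes, exempt the primary outcome from the start-to-closure sentence, and change its unit in the outcome table to mm/month.
2. In Data collection methods, before data are seen, define one rate per patient: the least-squares slope of antero-posterior anterior-tooth position on actual scan dates, from T0 through the interim models taken before closure. Name one landmark and one way of averaging left and right, the same in both arms. For patients who do not reach closure, use all available scans. State how a patient already closed at the first 4-weekly visit is scored, since no slope exists on this definition.
3. In Statistical Analysis item 2, compare arms with an unpaired Welch t-test and report the mean difference with its 95% confidence interval. Keep the paired test for within-group pre/post comparisons only.
4. In item 3, limit Kolmogorov-Smirnov and Shapiro-Wilk to checking the distribution of the rates.

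The cost is wording in four places. No visits, scans or patients are added, because the 4-weekly models are already planned. The drawback is that slopes are less precise with few scans, and faster closure leaves fewer scans; this is why the test should allow for unequal variances.

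### T_final has no measurable closure criterion and appears to be judged by unblinded treating staff, so the clock in the primary rate can be stopped with the arm known

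*Combined protocol and SAP*

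**What the plan says.** Section I) D], Outcomes, states that the primary outcome "is to monitor the rate of anterior segment retraction using both frictionless and friction methods". The same section sets the window: "All outcomes will be assessed as the difference between T_0 at the start of anterior segment retraction", ending at "T_{final} after complete space closure". The outcome table under the PICO question gives the tool and unit of the primary outcome as "Digital scanned dental models. mm", with no unit of time. No formula for the rate appears anywhere.

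Section I) E], Participant timeline, item 9 provides for visits every 4 weeks with interim impressions. Item 10 adds: "After complete space closure, the principle investigator will take post-retraction records for each participant".

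On masking, section II) D] says: "Blinding will not be possible for the operators during the application interventions and during the follow up visits". It makes the principal operator responsible for "appliance activation at follow up visits, dental impressions and acquisition of dental casts". Only the outcome assessors are blind. Two of them measure independently, and patient names are hidden on the pre and post models. Interim models are not mentioned there.

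Section III) A] has the principal investigator take models monthly, digitise them and place the landmarks on the pre, interim and post models. Section III) C] also gives that role the extraction of data from the models of every visit.

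**The concern.** A rate needs an elapsed time. If the time runs from T_0 to T_final, whoever decides that the space is closed also decides which visit ends it. Without a limit on residual space, one patient may be called closed with a small gap left while another is given one more activation. T-loops and power chains look different, so a judgement made at the chair is made with the arm known.

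This is separate from the rounding that 4-weekly visits cause. Rounding follows the same rule in both arms, whereas a judgement can differ by arm. The masking described in section II) D] covers the reading of models after the final date has been fixed, and gives the assessors no part in fixing it. At stake is detection bias in the primary outcome.

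**Working it through.** **Reading the text.** Three things were looked for.

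- *A criterion for closure.* The Outcomes section and timeline item 10 both name closure. Neither gives a gap in mm, a contact test, a rule for left and right or for the arches, a maximum duration, or independent confirmation.
- *Who decides.* Nobody is named. Timeline item 10 gives the final records to the principal investigator, and section II) D] gives visits, impressions and casts to the unblinded principal operator. That these are one role, and that this role declares closure, is inferred from the overlapping duties.
- *What the rate divides by.* This is not stated. The Outcomes section points to T_0 to T_final, while sections III) A] and III) C] also use the monthly models.

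**Illustration.** The plan states no sample size, SD, expected rate or duration, so there is no figure of its own to reproduce. The following inputs are assumptions, apart from the 4-week interval:

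- 4 mm of space to close
- closure called at visit 5 (20 weeks) or visit 6 (24 weeks)
- 4.345 weeks per month

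Let g be the space still open at visit 5 and closed by visit 6.

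- Rate if stopped at visit 5: (4 − g) / (20/4.345)
- Rate if stopped at visit 6: 4 / (24/4.345) = 0.724 mm/month
- Relative fall: 1 − (4/6) / ((4 − g)/5)

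| g (mm) | Rate at visit 5 | Rate at visit 6 | Fall |
|---|---|---|---|
| 0 | 4/4.603 = 0.869 | 0.724 | 16.7% |
| 0.25 | 3.75/4.603 = 0.815 | 0.724 | 11.1% |
| 0.50 | 3.5/4.603 = 0.760 | 0.724 | 4.8% |
| 0.67 | 3.33/4.603 = 0.724 | 0.724 | 0 |

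The fall vanishes where (4 − g)/5 = 4/6, that is, g = 4 − 3.33 = 0.67 mm. Beyond that, the later call gives the higher rate.

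The first row is a ceiling, because it assumes no movement in the extra visit. With v visits the ceiling is 1/(v + 1): 20% for v = 4, 14.3% for v = 6 and 11.1% for v = 8.

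**Scale.** The only SDs to hand are 0.46 and 0.34 mm/month. They come from the split-mouth trial of two T-loop alloys for canine retraction in the literature review, which is neither this tooth movement nor this comparison. Against them, the ceiling of 0.869 − 0.724 = 0.145 mm/month is 0.31 to 0.43 SD. The 0.5 mm case, 0.760 − 0.724 = 0.036 mm/month, is 0.08 to 0.11 SD. If half of one arm were affected, the arm mean would shift by at most about 8% (16.7%/2), or by about 2.4% (4.8%/2) in the 0.5 mm case.

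**The case against.** The strongest reply is that the rate need not depend on T_final. Models are taken and landmarked monthly, and a rate per interval or a slope fitted to them would hardly change with the visit called last. That stands as a possibility. However, the plan specifies no such rate, and the Outcomes section ends every outcome at T_final. The undefined rate and the undefined end-point are one gap and should be closed together.

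Second, the plan never says that the operator declares closure. That is correct; it is an inference, though the plan puts nobody else in a position to do it.

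Third, a residual gap shortens the measured distance as well as the time, and the models capture this. That also stands. A reader might infer from the arithmetic that one late call costs 17% of the rate, but the table shows that this is only the upper limit.

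A reader might also infer that masked model reading cannot cure the problem. The documents do not support that: models are kept from every visit, so a late call can be seen and corrected afterwards by masked readers. As written, masking is applied too late and to too few models.

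Finally, nothing in the documents suggests that the operator prefers either arm, so no direction of bias can be claimed.

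**Conclusion.** The point holds as a risk of bias that the plan leaves open. T_final closes the window for all outcomes and, on the natural reading, sets the time in the primary rate. Closure has no measurable criterion, and it appears to be judged by staff who know the arm. The last step is inferred from the division of duties, and the denominator is inferred from the stated window.

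Neither size nor direction follows from the documents. Under the assumed 4 mm and 5 versus 6 visits, the effect on one patient's rate ranges from a 17% fall at most, through about 5%, to none, depending on the space left at visit 5. The effect on the trial would also depend on how many patients were affected and whether this differed by arm. A claim that the primary result is biased by a given amount would go beyond the text. The change is still worth making, because the data it needs are already being collected.

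**What to change.** 1. State the rate formula and time unit: mm per month, as distance from T_0 to the analysis T_final divided by elapsed time from actual dates.
2. Define the analysis T_final as the first monthly model on which residual upper space on both sides is at or below a pre-set tolerance. Take distance and date from that same model.
3. Have the two existing masked assessors read residual space from coded pre, interim and post models. Coding must extend to the interim models, and sections III) A] and III) C] must be reconciled with II) D] on who landmarks and measures.
4. Choose a tolerance that assessor reliability supports. The plan flags disagreement between assessors only above one millimetre, so a finer tolerance needs a matching, tighter trigger for this distance.
5. If no scan meets the tolerance, use the last retraction scan with its measured distance and date.
6. Report a slope or fixed-interval rate from the monthly models as a sensitivity analysis.

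Clinical decisions stay as they are; only the end-point used in the analysis changes. The cost is protocol and SAP wording, coding of the interim models, the reassignment of some reading to the assessors, and one extra distance per side per scan. The 4-weekly rounding remains, under the same rule in both arms.
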